Amendment 2	14-Aug-2020	
Study endpoints updated to reflect a more rigorous efficacy threshold and the associated statistical methods were revised:
 
EASI-75 in the primary, key secondary and secondary endpoints was changed to EASI-90 to reflect a more rigorous efficacy threshold and statistical analysis methods have been revised.
 
EASI-90 in one of the secondary endpoints was changed to EASI-75.
 
Clarified that the estimand is PP-NRS4 (previously PP-NRS) since the endpoint is based on achieving at least a 4-point improvement in the severity of PP-NRS4 from baseline.
 
Sample size determination was updated to reflect the change from EASI-75 to EASI-90 in the primary and key secondary endpoints.
 
Clarified the CMH analyses method for the primary endpoint.
 
The tipping point analysis was changed to multiple imputations under the assumption of missing at random.
 
Per updated safety information, participants with increased risk of developing venous thromboembolism are excluded.
 
Inclusion criterion updated to require a clinical diagnosis of AD at least 6 months prior to Day 1 instead of at least 1 year. The duration of AD diagnosis has not been associated with the magnitude of treatment effect of other AD therapies. Given other current inclusion criteria, such as the requirement for recent inadequate response to topical therapies and/or treatment with (or consideration for) systemic therapies, reducing this inclusion criterion to 6 months is not anticipated to affect the study results.
 
Exclusion of prior use of dupilumab has been expanded to include all IL-4 and IL-13 antagonists. Dupilumab is

DOCUMENT HISTORY		
Document	Version Date	Summary and Rationale for Changes
		
an IL-4 and IL-13 antagonist and the criterion currently only excludes prior dupilumab use. By expanding the criterion to include the drug class, we avoid inadvertently enriching the patient population with participants who are non-responders to this mechanism.
 
Revised the baseline infection study terminology from “viral studies” to “infection studies” to allow for testing of other types of microorganisms.
 
Added additional infection studies sample to be taken at each study visit. This will allow for testing of SARS-CoV-2 or another emergent microbial organisms.
 
Language and an appendix were added to address COVID-19 and to describe alternative measures to be taken during public emergencies. This is in reference to the April 2020 PACL.
 
Added statement that if the participant experiences nausea, consideration should be given to administering oral study intervention with food. A food effect and lower incidence of nausea in a fed state has been observed in some participants.
 
Healthcare Resource Utilization (HCRU) assessment was moved from Week 16 to Week 12. There is a 3-month recall so if you assess at WK12 you are capturing the resource use from baseline to WK12 and then you capture the rest of the HCRU (more or less) when you assess at WK26. If we kept it at WK16 then we would miss the first 4 weeks post-baseline.
 
Added Asthma Control Questionnaire (ACQ) for participants with a prior diagnosis of asthma. Asthma is a common comorbidity in patients with AD and this questionnaire will provide information about whether abrocitinib has any effect on asthma control.
 
New clinical trial data from the abrocitinib study B7451013 and from the dupilumab CAFÉ and CHRONOS studies have been added to the protocol introduction.
 
Updates made per updated protocol template:
 
Clarified inclusion criterion 3 for female participants.

DOCUMENT HISTORY		
Document	Version Date	Summary and Rationale for Changes
		
Exploratory objective related to banked biospecimens was removed.
 
Section 8.3 Adverse events and Serious Adverse Events
 
Appendix 3 Adverse Events: Definitions and Procedures for Recording, Evaluating, Follow-up, and Recording.
 
Appendix 4 Contraceptive Guidance.
 
Appendix 10 Prohibited concomitant medications.
 
Changes made for improved instruction and process clarity:
 
Requirements for mental health professional assessments and recurrent suicidal ideation and behavior have been clarified.
 
The research supporting accelerometry has been described.
 
Added instruction for when to collect the eDiaries from participants.
 
Added instruction to clarify that banked biospecimens are collected for all participants (as local regulations and IRBs/ECs allow).
 
Dispensing and administration instructions for study intervention have been clarified.
 
Study-specific definitions of medication errors have been updated.
 
Tuberculosis testing procedures have been clarified.
 
Evaluation of hand eczema has been added to the rater qualifications and has been clarified.
 
Data collection requirements for adverse events of conjunctivitis have been added.

DOCUMENT HISTORY		
Document	Version Date	Summary and Rationale for Changes
		
Electronic diary review has been added to the Week 24 and Week 26 (EOT/ED) visits.
 
Clarified that the BSA for a subset of body regions (scalp, palms, and soles of feet) evaluated in EASI will be entered in the eCRF.
 
Temporary discontinuation timeframe updated for the injectable study intervention and requirement added for participants who need systemic rescue therapy to temporarily discontinue the study intervention while taking systemic rescue therapy. Participants need to temporarily discontinue the study intervention while taking systemic rescue therapy because the medications taken together could further suppress the participant’s immune system and, therefore, cause an increased safety risk.
 
Clarified that participants who use rescue therapy will be defined as “non-responsive” after start of rescue therapy.
 
Added isoniazid as a prohibited concomitant medication.
 
Clarified that the block randomization method will be used.
 
Recall period has been updated for the Medical Outcomes Study Sleep Scale (per the December 2019 PACL).
 
Anchors have been updated for the Skin Pain Numerical Rating Scale (per the December 2019 PACL).
 
Informal interim analyses for internal decision-making have been added.
 
Collection of prior marijuana use has been removed. The information would not be used in analyses.
 
Country-specific addition for the United Kingdom: Per agency requirement, added requirement for sites to contact participants who are WOCBP and are not entering the long-term extension study (B7451015) at 12 weeks after the last dose of study intervention to

DOCUMENT HISTORY		
Document	Version Date	Summary and Rationale for Changes
		
confirm adherence to contraception guidelines per protocol.
 
Country-specific addition for France: Requirements for study sites located in France have been added.
 
References have been updated.
 
Study acronyms have been updated.

Amendment 1 (Czech Republic only)	14-Jul-2020	
Country-specific changes for the Czech Republic:
 
Section 5.2: Patients with increased risk of developing venous thromboembolism are excluded. This exclusion criterion was added as a result of the updated April 2020 IB.
 
Section 6.5.2.: If a participant requires high potency topical therapy or systemic rescue therapy, they are to be permanently discontinued from the study intervention, have an End of Treatment visit and enter the 4-week follow-up period. This was a request from the Czech Republic.
 
Section 10.4.: Definition of postmenopausal female was revised to specify that the main condition is the absence of bleeding for 12 months without an alternative medical cause (removed portion of definition that allowed for participants age 60 or older to be considered postmenopausal). FSH level must be assessed in women in the postmenopausal range under the age of 60 and not using hormonal contraception or HRT (“may” changed to “must”). This was revised per the Czech Republic request and to be consistent with the current protocol template.

Original Protocol	04 November 2019	

This amendment incorporates all revisions to date, including amendments made at the request of country health authorities and IRBs/ECs.

TABLE OF CONTENTS

LIST OF TABLES	13
1. PROTOCOL SUMMARY	14
1.1. Synopsis	14
1.1.1. Estimands.....	17
1.2. Schema	21
1.3. Schedule of Activities (SoA).....	22
2. INTRODUCTION	29
2.1. Study Rationale	29
2.2. Background	30
2.2.1. Atopic Dermatitis.....	30
2.2.2. Clinical Efficacy and Safety of Dupilumab in AD	31
2.2.3. Clinical Efficacy and Safety of Abrocitinib in AD	33
2.3. Benefit/Risk Assessment.....	36
3. OBJECTIVES, ESTIMANDS AND ENDPOINTS	36
3.1. Estimands	39
3.2. Adjudication Committee	41
4. STUDY DESIGN.....	41
4.1. Overall Design.....	41
4.2. Scientific Rationale for Study Design	42
4.3. Justification for Dose	43
4.4. End of Study Definition	43
5. STUDY POPULATION	44
5.1. Inclusion Criteria.....	44
5.2. Exclusion Criteria.....	46
5.3. Lifestyle Considerations.....	52
5.3.1. Meals and Dietary Restrictions.....	52
5.3.2. Caffeine, Alcohol, and Tobacco	53
5.3.3. Vaccine and Exposure to Infections Guidelines	53
5.3.3.1. Participant Specific Recommendations.....	53

5.3.3.2. Guidance Regarding Household Contact Vaccine-Related Exposure	53
5.3.4. Surgery	53
5.4. Screen Failures	54
6. STUDY INTERVENTION.....	55
6.1. Study Intervention(s) Administered	55

1. PROTOCOL SUMMARY

1.1. Synopsis

Protocol Title: A PHASE 3B RANDOMIZED, DOUBLE-BLIND, DOUBLE-DUMMY, ACTIVE CONTROLLED MULTI-CENTER STUDY ASSESSING THE EFFICACY AND SAFETY OF ABROCITINIB COMPARED WITH DUPILUMAB IN ADULT PARTICIPANTS ON BACKGROUND TOPICAL THERAPY WITH MODERATE TO SEVERE ATOPIC DERMATITIS

Short Title: A Study to Assess the Safety and Efficacy of Abrocitinib Compared with Dupilumab in Adult Participants with Moderate to Severe Atopic Dermatitis

Rationale:

Atopic dermatitis (AD), also known as atopic eczema, is a common, chronic, inflammatory skin disorder characterized by flaky skin lesions, intense pruritus, and a general deterioration in quality of life. Over the past 50 years, AD has become more prevalent, especially in industrialized, temperate countries such as the United States (US).^{1,2} AD is one of the most common, chronic, relapsing childhood dermatoses, impacting 15-30% of all children in the US and many have disease that persists into adulthood with a lifetime prevalence of those affected in childhood reported to be 34%.³ Earlier reports indicated that, in up to 70% of cases, the disease greatly improves or resolves by late childhood, however more recent findings suggest that disease activity remains manifest for a prolonged period of time. Based on a total of 7157 participants enrolled in the Pediatric Eczema Elective Registry (PEER) study, comprising a total of 22,550 person-years, it was concluded that symptoms associated with AD seem to persist well into the second decade of life and likely longer.⁴ At every age, more than 80% of PEER study participants had symptoms of AD and/or were using medication to treat their AD.

Of the currently available therapies, none offers a cure; therefore, the main aims of existing treatments are to reduce skin lesions, reduce the occurrence of acute flares, to increase the time between relapses, and to reduce pruritus and the resulting sleep disturbance.^{5,6}

Non-medicated topical therapies include emollients. Medicated topical therapy for moderate to severe AD include topical corticosteroids (TCS) (eg, betamethasone, clobetasol, fluocinonide), topical calcineurin inhibitors (TCI) (eg, pimecrolimus, tacrolimus), and coal tar preparations. TCS are limited in terms of the treatment duration (eg, corticosteroid use is limited to 2 to 4 weeks) and the body region of treatment, due to consistent skin toxicities, as well as having risks associated with their broad immunosuppressive actions. TCI have a limited role as a second-line treatment, due to their limitations in the duration and the body region of treatment, inhibition of tumor surveillance in the skin, and safety concerns with malignancies. Crisaborole was approved as a medicated topical therapy (phosphodiesterase 4 [PDE4] inhibitor) in December 2016 by the Food and Drug Administration (FDA) for use in patients with mild to moderate AD and is being evaluated for approval in several other regions. Additional treatments generally reserved for severe AD include phototherapy (eg, ultraviolet A light [UVA] with or without psoralen, ultraviolet B-light [UVB] narrowband or broadband) and systemic agents (eg, corticosteroids, cyclosporine, recombinant interferon

gamma (IFN- γ), mycophenolate mofetil, methotrexate [MTX], azathioprine, intravenous immunoglobulin).⁷

There are a limited number of approved systemic treatments for moderate to severe AD and in the US, the only approved systemic drugs are corticosteroids and dupilumab. Per the American Academy of Dermatology (AAD) guidelines, the use of steroids should be avoided for the treatment of AD and should be exclusively reserved for acute, severe exacerbations and as a short-term bridge therapy to other systemic, steroid-sparing therapies.⁸

Dupilumab, an injectable human monoclonal antibody targeting interleukin (IL) -4 and -13, was approved by the FDA in March 2017 and received marketing authorization in Europe in September 2017, for the treatment of moderate to severe AD. Treatment with systemic corticosteroids has known and well documented adverse effects. Treatment with dupilumab has the risk of injection site reactions, allergic reactions, eye and eyelid inflammations and cold sores. Another potential limitation of dupilumab is the possibility for the development of antidrug antibodies, which may result in loss of efficacy over time and the development of safety concerns such as serum sickness-like reactions. Furthermore, dupilumab is delivered via subcutaneous injection, which may not be a method of administration tolerated well by all patients. During a 1-year, randomized, double-blinded study with dupilumab, in the dupilumab 300 mg every 2 weeks (marketed maintenance dose) plus TCS group, the estimated difference from placebo of the Investigator's Global Assessment (IGA) response rate and Eczema Area and Severity Index (EASI)-75 response rate ($\geq 75\%$ improvement from baseline in EASI score) were 26% and 46%, respectively. The placebo response rate for IGA and EASI-75 was 12% and 23%, respectively.⁹ The dupilumab response rate for a ≥ 4 -point improvement from baseline in PP-NRS4 at Week 2 and $\geq 90\%$ improvement from baseline in EASI score (EASI-90) was 18% and 40%, respectively.⁹ There is a need for therapies for those patients who do not respond to dupilumab or who after responding, fail to improve with dupilumab. The development of potential treatments with further improvements in efficacy remains desirable.

In Europe, cyclosporine is approved for use in patients with severe AD when systemic therapy is required. Cyclosporine use is associated with several undesirable side effects and due to its narrow therapeutic index, occasional therapeutic drug monitoring is recommended. Known adverse effects include infections, renal toxicity, hepatotoxicity, skin malignancies, lymphoma and other malignancies.

The predominant unmet medical need is for a conveniently administered therapy with an acceptable safety profile, for continuous and intermittent use, which is effective for moderate to severe AD. Patients with moderate to severe AD require other systemic treatment options beyond those which are currently approved. Abrocitinib is an oral tablet, providing a more convenient route of administration compared with the subcutaneous injection required for dupilumab and so it does not have the potential risk of injection site reactions. Unlike dupilumab, abrocitinib is a small molecule and there is no anticipated immunogenicity to abrocitinib, and so it is unlikely to generate antidrug antibodies and may be used intermittently.

Key cytokines implicated in the pathophysiology of AD include IL-4, IL-13, IL-31, and IFN- γ , and require Janus kinase 1 (JAK1) for signal transduction; this suggests that selective JAK1 inhibitors that modulate the activity of these cytokines represent a compelling approach to the treatment of inflammatory skin diseases such as AD.⁹ Broader inhibition of cytokines, including those important in the pathogenesis of AD, may result in an increased proportion of responders, with an acceptable safety profile.

Abrocitinib (formerly known as PF-04965842) is an orally bioavailable small molecule that selectively inhibits JAK1 by blocking the adenosine triphosphate (ATP) binding site. Abrocitinib has a high degree of selectivity for JAK1 when compared, in vitro, against other kinases: 28-fold selectivity over Janus kinase 2 (JAK2), >340-fold over Janus kinase 3 (JAK3) and 43-fold over tyrosine kinase 2 (TYK2), as well as a good selectivity profile over the broader range of human kinases. The selective inhibition of JAK1 will lead to modulation of multiple cytokine pathways involved in the pathophysiology of AD, including IL-4, IL-13, IL-31 and IFN- γ . Data from a Phase 2b proof of concept (POC) study (B7451006) that evaluated participants with moderate to severe AD have shown positive efficacy with both 100 and 200 mg, as well as an acceptable safety profile, sufficient to support further clinical development in a larger Phase 3 program.

Abrocitinib has been in Phase 3 development since December 2017 treating participants with moderate to severe AD with or without topical treatment. The first Phase 3 studies, B7451012 and B7451013, that evaluated 100 and 200 mg QD abrocitinib in participants with moderate to severe AD, which completed in 2019, reported statistically significant improvement in efficacy endpoints in both treatment groups compared to the placebo group, with an acceptable safety profile.

This Phase 3b study will investigate whether abrocitinib provides comparable or improved efficacy and safety compared with dupilumab in the treatment of moderate to severe AD.

Statistical Methods

The objective of the study is to demonstrate superiority of abrocitinib 200 mg once daily (QD) to dupilumab 300 mg every other week (Q2W) as measured by Peak Pruritus Numerical Rating Scale (PP-NRS4) response at Week 2 and EASI-90 response at Week 4. Additionally, this study is intended to demonstrate that abrocitinib 200 mg QD is non-inferior to dupilumab 300 mg Q2W and if non-inferior, to demonstrate the superiority to dupilumab as measured by EASI-90 response at Week 16. A total sample of 600 participants, with 300 participants randomized to abrocitinib, 300 participants randomized to dupilumab (1:1 randomization) is planned. The proposed sample size provides adequate power for all superiority hypotheses, as follows:

- **Week 2:** this sample size would provide at least 99% power to detect a difference assuming a difference of at least 25% in PP-NRS4 between abrocitinib and dupilumab and assuming the dupilumab response rate is 11% at Week 2.

- **Week 4:** this sample size will provide approximately 97% power to detect a difference assuming a difference of at least 15% in Week 4 EASI-90 between abrocitinib and dupilumab and assuming the dupilumab response rate is 12%.
- **Week 16:** this sample size will provide at least 99% power to show the difference is no more than 10% favoring dupilumab in EASI-90 at Week 16 (non-inferiority (NI) with a 10% margin), assuming the abrocitinib response rate is 53% and the dupilumab response rate is 43% at Week 16. This sample size will also provide approximately 70% power to demonstrate superiority of abrocitinib 200 mg QD to dupilumab as measured by EASI-90 response at Week 16.

The Type I error rate is set at 5% (two sided). The familywise Type I error rate (for testing the primary and key secondary endpoints) will be strongly controlled at 5% using a sequential testing approach. This is described in further detail in [Section 9](#) of the protocol and in the statistical analysis plan (SAP).

For analysis of the primary and key secondary endpoints, the Cochran-Mantel-Haenszel test adjusted by disease severity group (moderate and severe) will be used. For participants who drop out for any reason or use rescue therapy (Section 6.5.2) at any time during the treatment period, the response will be defined as “non-responsive” after that point.

For continuous endpoints, a mixed-effect model with repeated measures (MMRM) will be used. This model will include the factors (fixed effects) for treatment group, disease severity group, visit, treatment-by-visit interaction, and relevant baseline value. Within the framework of MMRM, the treatment at each time point will be derived from the MMRM model.

All participants who receive study intervention (safety population) will be included in the safety analyses. All the safety data will be summarized descriptively through appropriate data tabulations, descriptive statistics, categorical summaries, and graphical presentations.

Objectives, Estimands and Endpoints

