9.2. Sample Size Determination

This is a randomized, double-blind, double-dummy, active-controlled, multi-center study to assess the efficacy and safety of abrocitinib 200 mg QD compared with dupilumab (as per label guidelines) in adult participants on background topical therapy, with moderate to severe AD. The treatment duration is 26 weeks. A total of approximately 600 participants will be enrolled from approximately 220 sites globally. There are primary efficacy assessments at Week 2 and Week 4, and a key secondary efficacy assessment at Week 16. Efficacy and safety endpoints will be assessed throughout the entire study.

A total sample of 600 participants, with 300 participants randomized to abrocitinib, 300 participants randomized to dupilumab (1:1 randomization) is planned. The proposed sample size provides adequate power for all superiority hypotheses, as follows:

Week 2: This sample size would provide at least 99% power to detect a difference assuming a difference of at least 25% in PP-NRS4 between abrocitinib and dupilumab and assuming the dupilumab response rate is 11% at Week 2.

Week 4: This sample size will provide approximately 99% power to detect a difference assuming a difference of at least 15% in Week 4 EASI-90 between abrocitinib and dupilumab and assuming the dupilumab response rate is 12%.

Week 16: this sample size will provide at least 99% power to show the difference is no more than 10% favoring dupilumab in EASI-90 at Week 16 (non-inferiority (NI) with a 10% margin), assuming the abrocitinib response rate is 53% and the dupilumab response rate is 43% at Week 16. This sample size will also provide approximately 70% power to demonstrate superiority of abrocitinib 200 mg QD to dupilumab as measured by EASI-90 response at Week 16.

While the power to detect a difference at the early time points of 2 and 4 weeks and non-inferiority at week 16 is strong implying a decrease sample size could be used, the power to demonstrate superiority at week 16 requires the larger number of participants. Superiority at week 16 is a valuable endpoint for the scientific community and prescribers justifying the larger sample size. In addition, the study design avoids exposing participants to the use of placebo alone. While a larger number of participants are utilized, they will be guaranteed treatment on 1 of the 2 active treatment arms, which allows for potential benefit for all participants included in the study.

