Week 4: This sample size will provide approximately 99% power to detect a difference assuming a difference of at least 15% in Week 4 EASI-90 between abrocitinib and dupilumab and the dupilumab response rate is 12%.

Week 16: This sample size will provide at least 99% power to show the difference is no more than 10% favoring dupilumab in EASI-90 at Week 16 (non-inferiority [NI] with a 10% margin), assuming the abrocitinib response rate is 53% and the dupilumab response rate is 43% at Week 16. This sample size will also provide approximately 70% power to demonstrate superiority of abrocitinib 200 mg QD to dupilumab as measured by EASI-90 response at Week 16.

While the power to detect a difference at the early time points of 2 and 4 weeks and non-inferiority at week 16 is strong implying a decrease sample size could be used, the power to demonstrate superiority at week 16 requires the larger number of participants. Superiority at week 16 is a valuable endpoint for the scientific community and prescribers justifying the larger sample size. In addition, the study design avoids exposing participants to the use of placebo, i.e., will be guaranteed treatment on 1 of the 2 active treatment arms, which allows for potential benefit for all participants included in the study.

The familywise Type I error rate (for testing the primary and key secondary endpoints) will be strongly controlled at 5% (2-sided) using a sequential multiple testing procedure outlined in [Section 5.1](#).

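### The synopsis gives 97% power for the Week 4 EASI-90 primary endpoint; Protocol Section 9.2 and the SAP give 99% on the same inputs, and only 99% reproduces

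*Protocol*

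**What the plan says.** The Statistical Methods part of the protocol synopsis (Section 1.1) fixes the size of the trial: "A total sample of 600 participants, with 300 participants randomized to abrocitinib, 300 participants randomized to dupilumab (1:1 randomization) is planned". For Week 4 it then says that "this sample size will provide approximately 97% power to detect a difference assuming a difference of at least 15% in Week 4 EASI-90", with a dupilumab response rate of 12%.

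Protocol Section 9.2 repeats the list of power statements with the same sample size, difference and dupilumab rate, but its Week 4 entry reads: "This sample size will provide approximately 99% power to detect a difference assuming a difference of at least 15% in Week 4 EASI-90". SAP Section 2.2, under Sample Size Determination, agrees with Section 9.2: "This sample size will provide approximately 99% power", again for a difference of at least 15 points over a 12% dupilumab rate.

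The type I error is 5% two-sided in the synopsis, in Protocol Section 9.4.2 and in SAP Section 5.1. All of these statements are current text; none belongs to a summary of changes.

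**The concern.** Sample size, allocation, control rate, difference and type I error are identical in the three places, so the power must be identical too. A reader who meets both figures cannot tell which calculation supports the design, or whether the 97% rests on an assumption that the text leaves out, such as a smaller evaluable sample or a smaller effect.

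The endpoint is not a minor one. Week 4 EASI-90 is one of two primary endpoints and second in the fixed testing sequence, so both Week 16 tests depend on it. Its power should be stated once and correctly.

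**Working it through.** **Inputs**

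- n = 300 per arm, 1:1 (synopsis; Protocol 9.2; SAP 2.2).
- Dupilumab rate p₂ = 0.12 (same three places).
- Difference d = 0.15 (same three places), so abrocitinib p₁ = 0.12 + 0.15 = 0.27.
- Two-sided α = 0.05, z = 1.96 (synopsis; Protocol 9.4.2; SAP 5.1).
- Planned test: "the Cochran-Mantel-Haenszel test adjusted by disease severity group (moderate and severe) will be used". No stratum-specific rates are given, so an unstratified two-proportion calculation is used as an approximation.

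**Power at the stated inputs**

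Unpooled normal approximation, power = Φ(d/SE₁ − z):

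- SE₁ = √[(0.27×0.73 + 0.12×0.88)/300] = √[(0.1971 + 0.1056)/300] = √0.001009 = 0.03176
- 0.15/0.03176 − 1.96 = 2.76
- Φ(2.76) = 0.997, i.e. **99.7%**

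Pooled variance under the null, power = Φ((d − z·SE₀)/SE₁):

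- p̄ = (0.27 + 0.12)/2 = 0.195
- SE₀ = √[2×0.195×0.805/300] = 0.03235
- (0.15 − 1.96×0.03235)/0.03176 = 2.73
- Φ(2.73) = 0.997, i.e. **99.7%**

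Other standard choices at the same inputs:

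| Method | Power |
|---|---|
| Continuity-corrected | 99.56% |
| Arcsine | 99.71% |
| Chi-square test, exact binomial power | 99.71% |
| Fisher exact | 99.66% |

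Every method lands above 99.5%. That agrees with approximately 99% and lies more than 2.5 points above 97%.

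**Does the same method reproduce the other stated powers?**

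| Test | Assumed rates | Stated | Recalculated |
|---|---|---|---|
| Week 2 PP-NRS4 superiority | 36% vs 11% | at least 99% | >99.9% |
| Week 16 EASI-90 non-inferiority, 10% margin | 53% vs 43% | at least 99% | 99.8% |
| Week 16 EASI-90 superiority | 53% vs 43% | approximately 70% | 68.9% |

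It does, so the synopsis figure for Week 4 is the only one that fails.

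**What would give 97%?**

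- Sample size: about 200 per arm (97.1% unpooled at 200; the pooled formula needs 203, or 216 with continuity correction).
- Effect: about 12 points at 300 per arm (97.2% unpooled, 97.1% pooled).
- Control rate: near 30% with the 15-point difference kept (96.8% at 30%).

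The documents state none of these for Week 4.

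**Could an unstated allowance for dropout explain it?** Dropouts count as non-responders, so both rates can be multiplied by (1 − dropout):

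| Dropout (assumed) | Power, pooled |
|---|---|
| 5% | 99.5% |
| 10% | 99.2% |
| 15% | 98.8% |

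Cutting the evaluable sample by 20%, to 240 per arm, still leaves 98.7% (98.3% with continuity correction). Halving α to a two-sided 2.5% gives 99.3%. A two-sided 1% level gives 98.2%, but the documents set 5%.

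**The case against.** The strongest reply is that nothing depends on the wrong number. The testing sequence, α, endpoint, test and sample size are the same whichever figure is printed. The gatekeeping role of Week 4 turns on its true power, which a misstated synopsis figure does not change. The 97% understates power, so it hides no shortfall. Both Section 9.2 and the SAP say that power for Week 2, Week 4 and Week 16 non-inferiority is high enough to allow a smaller trial, and that Week 16 superiority sets the sample size. The detailed section and the SAP already carry 99%. All of this stands, and it makes the correction editorial.

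Two smaller points also stand. The planned test is stratified and the check is not, though stratification is unlikely to alter the conclusion. And approximately 99% is itself rounded down from 99.7%: an exact 99% would need only about 252 per arm by the pooled formula. It is compatible with the inputs as an approximate statement, whereas 97% is not.

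None of this removes the contradiction or supplies inputs under which 97% would be right.

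**Conclusion.** The concern holds. The synopsis power for Week 4 EASI-90 is wrong on its own inputs: 97% stated against 99.6–99.7% recalculated, a gap of about 2.6 to 2.7 percentage points. As type II error, that is 3% implied against 0.3–0.4%. Protocol Section 9.2 and SAP Section 2.2 have the supportable figure.

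The conclusion assumes rates of 27% and 12%, 300 per arm, a two-sided 5% level and an unstratified comparison. It does not depend on which standard two-proportion method is used. The design is not affected, but the figure should be corrected because it concerns a primary endpoint and contradicts the protocol's own sample size section.

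**What to change.** In the Week 4 item of the synopsis, change the power to approximately 99%. Use that wording rather than at least 99%, so that it matches Protocol Section 9.2 and SAP Section 2.2 exactly. If 97% was intended, state the assumptions behind it and bring the other two places into line.

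The cost is one figure in the synopsis, at the next amendment or by administrative letter. No analysis, sample size or SAP text changes.
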